9.4.4 SAFETY ANALYSES

Descriptive statistics will be presented per study group for all safety parameters.

The primary safety variable, the cumulative incidence (and 95% CI) of adverse events (AEs) reported throughout the study in each of the study groups, will be presented in tabular format and will include incidence tables by severity and relationship to study device and/or procedure.

Adverse event rates will be compared between the study groups with a Fisher's exact test.

Serious adverse events will be listed and discussed individually.

Treatment tolerability will be presented. The number and percent of subjects who fail to complete the study and the number and percent of subjects who fail to complete the study because of adverse events will be presented.

In addition, listings of all safety measures and device deficiencies will be produced.

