4.4 END OF STUDY DEFINITION

A participant is considered to have completed the study if he or she has completed all phases of the study including the last visit or the last scheduled procedure shown in the Schedule of Activities (SoA; § 1.3). The end of the study is defined as completion of the last visit shown in the SoA for the last subject in the trial¹⁹.

¹⁹ 42 CFR Part 11 § 11.10(a)(3) “study completion date”; ISO 14155:2020 § 8.1

The study primary completion date,²⁰ is the date that the final subject was examined or received an intervention for the purposes of final collection of data for the primary 90 days outcome, whether the trial concluded according to this protocol or was terminated.

For the purposes of regulatory submissions to support market approval, data through 90 days is intended to support safety and effectiveness and submission is planned when the last subject enrolled is through the 90-day study period. Additional longer-term data is exploratory in nature.

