7 STUDY INTERVENTION DISCONTINUATION AND PARTICIPANT DISCONTINUATION/WITHDRAWAL

7.1 DISCONTINUATION OF STUDY INTERVENTION

Any symptoms of treatment-emergent clinical deterioration in subject's condition requiring intervention of the medical team to alleviate these symptoms and qualifying for toxicity Grade 3 (or higher) on the CTCAE v.5.0 scale will result in a halt of administration of the study intervention for that treatment session; halting for a longer period of time will occur only if deemed necessary by the Investigator.

In general, discontinuation of administration of the study intervention, for any reason, does not mean discontinuation from the study, and the remaining study procedures should be completed as indicated by the study protocol, unless informed consent is withdrawn. If a clinically significant finding is identified (including, but not limited to changes from baseline) after enrollment, the Investigator or qualified designee will determine if any change in subject management is needed. Any new clinically relevant finding will be reported as an AE. For requirements on reporting of adverse events, serious adverse events and unanticipated problems please refer to §§ 8.3.5, 8.3.6, and 8.4.2, respectively.

The data to be collected at the time of discontinuation of administration of the study intervention will include the date and reason for discontinuation and any data on the adverse event(s), if applicable.

Women who become pregnant during the trial will continue to be assessed, including assessment of pregnancy outcomes, and investigational device administration will be discontinued. Further provisions on reporting of pregnancy, including period of reporting are in § 8.3.9.

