7.2 PARTICIPANT DISCONTINUATION/WITHDRAWAL FROM THE STUDY

Participants are free to withdraw from participation in the study or discontinue the study intervention at any time upon request. Those wishing to discontinue participation do not have to provide a reason; however, when appropriate, the site investigator should discuss the study, informed consent, and any on-going risks and benefits to continued participation with the participant.

In addition to discontinuation of administration of the study intervention (section 7.1), subject participation in the study may be terminated by the Investigator or the Sponsor if any one or more of the following conditions are met:

- occurrence of an unexpected serious adverse event;

	The efficacy of a frequency-tuned electromagnetic field treatment in facilitating the recovery of subacute ischemic stroke patients – a pivotal study		
	No. BQ5	Ver. 4	Page 58 of 150

- pregnancy;
- loss to follow-up (refer to § 7.3 for accompanying instructions); health conditions that require treatment that might affect the procedure and/or its outcome;
- significant protocol deviation (please refer to § 10.1.10) or noncompliance, either on the part of the subject or Investigator. These will include (but not limited to):
 - o enrollment in violation of the study eligibility criteria;
 - o performing the trial procedure not as prescribed in the BQ 2.0 IFU;
 - o other ethical or clinical considerations at the discretion of Investigator.
 - o enrollment in another interventional study overlapping with the period of participation in this study.

Data collected prior to withdrawal of consent will remain in the study database, but no further data will be collected on those who withdraw. Follow up on serious adverse events that are not resolved by the time that the subject leaves the study will be handled as defined in § 8.3.4. Follow up on pregnancy outcome will be handled as defined in § 8.3.9.

Withdrawn/discontinued randomized subjects will not be replaced.

If a subject withdraws from the clinical investigation, the reason(s) shall be recorded. Withdrawals will be recorded, analyzed, and reported to local IRBs/ECs as required.

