9.4.10 ADHERENCE AND RETENTION ANALYSES

The numbers of subjects who were enrolled and completed each visit of the study will be provided, as well as the reasons for all enrollment discontinuations, grouped by major reason (eg,

⁵⁰ The compliance analysis will be conducted as an exploratory sensitivity analysis assessing the correlation of number of completed treatments with the primary efficacy endpoint.

	The efficacy of a frequency-tuned electromagnetic field treatment in facilitating the recovery of subacute ischemic stroke patients – a pivotal study		
	No. BQ5	Ver. 4	Page 86 of 150

lost to follow-up, adverse event, poor compliance). A list of discontinued patients, protocol deviations, and patients excluded from the efficacy analysis will be provided as well. The effects of non-compliance, dropouts, and possible covariates such as age and sex will be assessed to determine the impact on the general applicability of results from this study.

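### Treatment tolerability in section 9.4.4 is summarised by failure to complete the study, so subjects who stop the device for an adverse event but stay in follow-up, as section 7.1 asks, are missed on the ordinary reading

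*Protocol*

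**What the plan says.** Section 9.4.4 (Safety Analyses) names treatment tolerability and follows it with two counts. The first is in "Treatment tolerability will be presented. The number and percent of subjects who fail to complete the study". The second is that "the number and percent of subjects who fail to complete the study because of adverse events will be presented". Both refer to completing the study, and neither mentions completing or stopping the device.

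Section 4.4 defines completion: "A participant is considered to have completed the study if he or she has completed all phases of the study including the last visit". As an alternative marker it gives the final procedure listed in the Schedule of Activities. The last visit in that schedule is Day 180. No number of treatment sessions is named.

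Section 7.1 states that, in general, "discontinuation of administration of the study intervention, for any reason, does not mean discontinuation from the study", and that the remaining procedures should be completed unless consent is withdrawn. It adds: "The data to be collected at the time of discontinuation of administration of the study intervention will include the date and reason for discontinuation", together with any adverse event data.

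Section 7.2 handles leaving the study separately: "subject participation in the study may be terminated by the Investigator or the Sponsor" under listed conditions, which include an unexpected serious adverse event.

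Section 9.4.10 covers retention and will give the "reasons for all enrollment discontinuations, grouped by major reason". The compliance analysis, described in footnote 50 to the subgroup list in section 9.4.7, is about efficacy: "assessing the correlation of number of completed treatments with the primary efficacy endpoint".

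**The concern.** A tolerability summary should show how many subjects could not or would not continue the treatment, and how many of them stopped because of an adverse event. Section 9.4.4 counts a different event, leaving the study. The two would coincide if stopping the device meant leaving the study, but section 7.1 is written so that normally it does not.

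The direction of the error is known. Retaining subjects who stop treatment is good practice, yet here each retained subject drops out of the tolerability count. A well-run trial would report a rate of adverse-event-related non-completion near zero whatever the true rate of stopping the device. Characterising the safety profile is a stated objective of this pivotal trial, and section 4.4 says the Day 90 data are meant to support safety in a market submission, so readers may rely on the figure.

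**Working it through.** The protocol states no figure here that can be reproduced, so the check sets the sections side by side.

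**Step 1: follow one subject through the text.** A subject starts treatment, has an adverse event, stops the device for good, and attends every later assessment.

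| Section | What it makes of this subject |
|---|---|
| 7.1 | Study intervention discontinued; date and reason recorded; still in the study |
| 7.2 | Not withdrawn, unless the investigator or sponsor also ends participation |
| 4.4 | Completer, if completion is judged by the last visit or procedure; non-completer, if completing all phases includes finishing treatment |
| 9.4.4 | On the first reading of 4.4, in neither of the two tolerability counts |
| 9.4.10 | Not an enrollment discontinuation |

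**Step 2: express the shortfall.** Let x be the share of subjects in an arm who stop the device for an adverse event, and s the share of those who stay to the visit that defines completion. On the ordinary reading of section 4.4:

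- true rate of stopping for an adverse event = x
- rate shown by section 9.4.4 = x(1 − s)
- amount missed = x·s

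At s = 1, full adherence to section 7.1, nothing is captured. At s = 0 everything is captured. The documents give neither x nor s.

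**Step 3: illustrate with assumed values.** With 150 randomized at 1:1 there are 75 per arm. Assume 6 stop for adverse events, so x = 6/75 = 8.0%.

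| Assumed number staying, of 6 | s | Rate shown |
|---|---|---|
| 0 | 0 | 6/75 = 8.0% |
| 3 | 0.5 | 3/75 = 4.0% |
| 5 | 5/6 | 1/75 = 1.3% |
| 6 | 1 | 0/75 = 0% |

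The 8% is an illustration and not an expectation. Section 2.3.1 reports no device- or procedure-related events in the sponsor's trials to date.

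**Step 4: look for the count elsewhere.** The rest of section 9.4.4 gives adverse event incidence by group, severity and relationship, a Fisher's exact comparison, and listings. Sections 8.2 and 8.3.5 record the action taken for each adverse event, but no section says that it will be tabulated. Section 9.4.10 gives the numbers completing each visit, and sections 7.3, 8.1.1.3 and 8.1.1.5 treat sessions as visits, so a fall-off across sessions may be visible there. That section does not say the numbers will be split by arm or tied to a reason for stopping the device. No section plans a count by arm of device stops due to adverse events.

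**Step 5: which visit counts as completion.** Section 4.4 points to the last scheduled visit, Day 180. Section 9.1 calls the visit at 90 ± 15 days the end of study. Section 9.4.6 times the interim analysis by 78 evaluable subjects completing the study, while the synopsis gives that trigger as completion of the 90-day visit by 61% of evaluable participants (78/128 = 60.9%). Section 9.4.9 puts safety through 180 days under exploratory analyses. So the text does not settle whether a missed Day 180 contact is a failure to complete in section 9.4.4. If it were, an assumed 5–10% of 75 missing only that contact would add 3.75 to 7.5, about 4 to 8 subjects per arm. Section 6.1.2 ends sessions by the day before the Day 90 visit, so those subjects would say nothing about tolerating the device.

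**The case against.** The best counter-argument is the wording of section 4.4. It asks for all phases of the study to be completed, and the synopsis has a named treatment phase with 45 sessions. Read literally, a subject who stops the device for good has not completed every phase and is counted in section 9.4.4. This reading cannot be excluded, so a flat statement that such subjects are never counted would go too far. It is not the ordinary reading, because section 4.4 sets no session requirement and section 7.1 separates the two events. Even if it were adopted, the count would still mix treatment stops with losses to follow-up.

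Subjects who stop the device and also leave the study are counted on either reading. Section 7.1 says in general and allows for withdrawal of consent, and section 7.2 lets the investigator or sponsor end participation. The gap concerns only those who stay.

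A reader might infer that a difference between arms in stopping for adverse events would be wholly hidden. The documents do not support that: adverse event incidence by arm, listings, recorded action taken and per-visit completion counts all carry some of the information. The difference would be obscured.

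A reader might also infer that the measure is shown to misclassify in both directions, because a subject with all sessions who misses only Day 180 counts as a failure. That depends on a meaning of completion that section 9 does not use consistently, so it is unclear and not established.

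Finally, section 9.4.1 sends detailed methods to the SAP and gives it precedence, and tolerability is not an endpoint. Both are true. But section 9.4.4 itself states the two counts, so this is more than detail left for later. The absence of any effect on an endpoint bears on how serious the point is, and does not remove it.

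**Conclusion.** The point holds in limited form. Section 9.4.4 names treatment tolerability but counts study non-completion, and section 7.1 keeps the two apart. On the ordinary reading of section 4.4, the summary understates adverse-event-related treatment discontinuation by x·s, which rises with adherence to section 7.1 and reaches the whole of x when every such subject stays. The size cannot be derived from the documents; 8.0% against 1.3%, and 4 to 8 subjects per arm for missed Day 180 contacts, are assumed illustrations only.

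The conclusion rests on reading completion as reaching the last visit or procedure. If completing all phases is taken to include treatment, the fault becomes one of ambiguity and mixing, which the same change cures. The safety endpoints (serious procedure- or device-related adverse events, and device deficiencies), the efficacy analysis and the interim decision rules are untouched. This is a reporting correction worth making, not a threat to the trial's main conclusions.

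**What to change.** In section 9.4.4, report by arm on the safety analysis set (SAF) the number and percent of subjects who permanently discontinue the study intervention before completing the planned sessions, overall and because of an adverse event, with the number of sessions completed at stopping. Use the date and reason already collected under section 7.1.

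Move study non-completion to section 9.4.10 as a retention summary, and state whether it refers to Day 90 or Day 180. One sentence should say whether completing the study, as defined in section 4.4, includes completing the treatment phase.

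The cost is a short text change and one extra table. No new data are needed, and no clinical rule, sample size or efficacy analysis changes. The reported tolerability figure may look less favourable.

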9.4.5 BASELINE DESCRIPTIVE STATISTICS

Demographic and baseline condition related characteristics (such as measurements taken at screening) will be tabulated and compared between the study groups by data type. Continuous variables will be summarized by a mean, standard deviation, minimum, median, and maximum and categorical variables by a count and percentage. The statistical evaluation of baseline characteristics will include all available data from the ITT set.

9.4.6 PLANNED INTERIM ANALYSES

One interim analysis is planned, after 78 evaluable subjects will complete the study.

Planning an interim analysis that permits an increase in the sample size as described below does not additionally inflate the type I error (116-119). In addition, the final analysis is performed using the conventional test as appropriate for the statistical hypothesis.

Depending on the outcome of the interim analysis, the study will either continue to the originally planned sample size, stop for futility or continue with an increased sample size. These decisions will be made based on the conditional power (CP), which is defined as the conditional probability that the result will exceed a critical value at the interim given the observed effect size.

Note that the interim analysis will be conducted on mITT analysis set.

	The efficacy of a frequency-tuned electromagnetic field treatment in facilitating the recovery of subacute ischemic stroke patients – a pivotal study		
	No. BQ5	Ver. 4	Page 83 of 150

After all the relevant data is entered into the database, and the database is cleaned, a soft lock to the database will be performed. An independent unblinded statistician (not the study statistician) will perform the assessments described. Only the unblinded statistician and members of the DSMB will be exposed to the interim report. The members of the data monitoring team of the Sponsor, if such a team is designated, will be limited to individuals with relevant expertise who are independent from the personnel involved in conducting or managing the trial. Only these members may have access to the unmasked information of the interim analysis. Investigators and Sponsor representatives will only be informed of the recommendation to continue or to discontinue the trial, or to implement other modifications in the trial procedure and design suggested by the DSMB, and based on the interim results. The unblinded statistician who is responsible for conducting the interim analyses should ensure that the unmasked data is not available to any unauthorized person within or outside the company.

Decision Rules

The study will either continue to the originally planned sample size if the result is “favorable”, stop for futility if the result is “unfavorable” or an increase will be made to the sample size if the result is “promising”. These decisions will be made based on the conditional power (CP), defined as the conditional probability that the result will exceed a critical value at the interim given the observed effect size $\hat{\delta}_1$ = difference between mean change from baseline mRS score for the BQ 2.0 versus sham groups at the interim look.

Notation:

- n1= sample size at interim analysis.
- n2= original sample size calculated based on assumed effect size.

nmax = the highest sample size the company is willing to use, nmax = 292 subjects (344 randomized including an allowance for a 15% dropout), and is based on a potential smaller effect size of ~0.33.

CPmin = is the calculated minimum CP based on the ratios nmax/n2, n1/n2 and the target study power (80%).

The following are the decision rules for the interim analysis which will be performed upon accrual of ~61% (n1/n2) of the originally planned sample size, ie, 78 evaluable subjects. These depend on the zone into which CP falls at the interim, the calculated CPmin, the maximum sample size designated for the study and the % of the originally planned sample size at which the interim analysis will be performed. Following this principle does not inflate the Type I error.

	The efficacy of a frequency-tuned electromagnetic field treatment in facilitating the recovery of subacute ischemic stroke patients – a pivotal study		
	No. BQ5	Ver. 4	Page 84 of 150

- If the result is “Unfavorable”, ie, $CP < CP_{min} = 32.7375\%$, ie, interim result is so disappointing that it is not worth increasing the sample size to retrieve conditional power, stop the trial for futility.
- If the result is “Promising”, ie, $32.7375\% \leq CP < 80\%$ for the primary endpoint, the sample size is increased to recover the targeted power of 80%. The sample size used will be either the new calculated sample size based on the conditional power (117) or the predetermined maximum sample size of 292 (344 randomized including an allowance for a 15% dropout) subjects, whichever lower.
- If the result is “Favorable”, ie, $CP \geq 80\%$ for the primary endpoint, the interim results are sufficiently favorable and the trial continues to the original sample size planned of 128 (150 randomized including an allowance for a 15% dropout) without the need to adaptively increase the sample size.

Controlling the Alpha Level for the Primary Endpoint

The overall alpha level for this study is 5%. Planning an interim analysis that permits an increase in the sample size as described above does not inflate the type I error (116, 118, 119), which means that the testing of the primary endpoint will be at a 5% level of significance.

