9.2 SAMPLE SIZE DETERMINATION

A sample size is calculated to test the null hypothesis with 80% power at a 5% two-sided level of significance using a two sample-t-test for simplicity, even though the main statistical analysis may employ a statistically more powerful model-based approach. The estimates used for the mean and standard deviation of the changes from baseline to day 90 are taken from the literature as well as company pilot study data. In the pilot study, the mean change in mRS score from baseline to week 9 in the treatment group was -2.5 (SD=0.66) versus -1.3 (SD=0.46) in the sham group. In the literature a difference of 0.06 points on the mRS between treatment groups is considered clinically meaningful (114). As powering the trial to detect this difference would yield infeasibly large sample sizes, sample size projections were based on detecting a difference as low as 40% of the difference seen in the pilot trial = 0.5-point. To detect a 0.5-point difference between the groups with 80% power at a 5% level of significance using a standard deviation of 1 point and 1:1 allocation ratio, the calculated sample size (PROC POWER in SAS V9.4) is 128 participants in total, 64 participants in each arm. Allowing for a 15% dropout, 150 participants should be randomized.

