9.4.2 ANALYSIS OF THE PRIMARY ENDPOINT

The primary endpoint, mRS change from baseline (day 4-21 post-stroke) to 90 days post-stroke, will be compared between the treatment groups using repeated measures analysis of covariance (ANCOVA, SAS® MIXED procedure).

The model will include the following fixed effects: treatment group, visit [categorical – midterm follow-up visit (± 4 days from 20th treatment) and Day 90 follow-up visit (day 90 ± 15 days post-stroke)], treatment group by visit interaction with baseline mRS and age entered as covariates. Age will be entered as a continuous variable so that the potential for co-linearity problems will be minimized. Center will be entered as a random effect. The treatment group by site interaction will be evaluated as well, but not as part of the principal statistical evaluation.

The compound symmetry covariance structure will be used. If the model does not converge, then either the unstructured or autoregressive (AR1) (whichever model has the lower Akaike information criterion statistic) covariance matrix structure will be used instead. At this time point (up to 3 months post stroke), we do not expect a high proportion of dropouts, as a placebo effect of the sham treatment is expected and was taken into consideration in the design of the study. Thus, any missing data at this time point can be considered missing at random. Therefore, since likelihood based repeated measures is also an imputation method, for this evaluation no other method of imputation of missing data is considered beyond the model estimates. Nevertheless, should the missing at random assumption prove to be incorrect, a sensitivity analysis using methods for data imputation may be performed, such as last observed value (LOV) of that endpoint (115). The LOV is defined as the last available post baseline visit data up to and including the last treatment visit or termination visit. Additionally, we may consider multiple

	The efficacy of a frequency-tuned electromagnetic field treatment in facilitating the recovery of subacute ischemic stroke patients – a pivotal study		
	No. BQ5	Ver. 4	Page 81 of 150

imputation using a model incorporating key baseline prognostic features as well as the last post-randomization if deemed necessary.

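### The 80% power in Protocol 9.2 is a fixed-sample figure; with the futility stop in 9.4.6 applied as written, power at 0.5 points is about 77-79%

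*Protocol*

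**What the plan says.** Protocol 9.2 states: "A sample size is calculated to test the null hypothesis with 80% power at a 5% two-sided level of significance". It assumes a 0.5-point difference, SD 1 and 1:1 allocation, which gives 64 per arm (128 evaluable, 150 randomized). It adds that a t-test is used for simplicity, "even though the main statistical analysis may employ a statistically more powerful model-based approach". Section 9.4.2 specifies that model: repeated measures with "treatment group by visit interaction with baseline mRS and age entered as covariates".

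Section 9.4.6 sets one interim analysis at 78 evaluable patients, with three outcomes decided by conditional power (CP) at the observed effect:

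- **CP below CPmin = 32.7375%:** "interim result is so disappointing that it is not worth increasing the sample size to retrieve conditional power, stop the trial for futility".
- **CP from CPmin to below 80%:** the sample size is raised to bring power back to 80%, capped at 292 evaluable.
- **CP of 80% or more:** "the trial continues to the original sample size planned of 128".

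CPmin is defined from nmax/n2, n1/n2 and the 80% target. The final test is the conventional one at 5%. On who decides, 9.4.6 also says: "Investigators and Sponsor representatives will only be informed of the recommendation to continue or to discontinue the trial". Section 10.1.6 lists interim futility among the grounds on which the DSMB may suggest stopping early.

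**The concern.** The power calculation describes a trial that always runs to 128. Under 9.4.6 a trial below CPmin does not run to 128, because continuation at that size is provided only for a favorable result. Every such trial counts as a failure, including those that would have recovered, and 9.2 makes no allowance for this.

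The threshold was also built for another purpose. CPmin is the lowest conditional power at which the sample size can be raised to nmax while the conventional test stays valid. It does not measure whether finishing at 128 is hopeless. The result is that an observed difference of about 0.30, some 60% of the design effect, ends the trial.

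At stake is whether the power quoted for a pivotal trial belongs to the design that will be run, and whether the sponsor knows what the stopping rule costs.

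**Working it through.** **Inputs.** From 9.2: difference 0.5, SD 1, two-sided 5%, n2 = 128. From 9.4.6: n1 = 78, nmax = 292, target 80%, CPmin = 32.7375%.

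**1. The fixed-design figure.** The noncentral t calculation with 64 per arm gives 80.1%. The normal approximation is Φ(0.5/√(4/128) − 1.96) = Φ(2.828 − 1.960) = 80.7%. The 80% in 9.2 reproduces.

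**2. CPmin.** The conventional test remains valid at the raised size N if b(z1, N) ≤ 1.96, where

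b = {√[(N − n1)/(n2 − n1)] × (1.96√n2 − z1√n1) + z1√n1} / √N.

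At N = 292 and z1 = 1.3118:

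- 1.96√128 − 1.3118√78 = 22.174 − 11.586 = 10.589
- √(214/50) = 2.0688
- b = (2.0688 × 10.589 + 11.586)/17.088 = 1.960

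Conditional power at that point is

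CP = 1 − Φ[(1.96√n2 − z1√n1)/√(n2 − n1) − z1√(n2 − n1)/√n1] = 1 − Φ(1.4975 − 1.0503) = 32.74%.

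This matches the protocol's figure. The interim standard error is √(4/78) = 0.2265, so the bound is an observed difference of 1.3118 × 0.2265 = 0.297. In the same way, CP = 80% falls at z1 = 1.9406, a difference of 0.439.

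**3. Zones at a true effect of 0.5.** The mean of z1 is 0.5/0.2265 = 2.208.

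- Unfavorable: Φ(1.312 − 2.208) = 18.5%
- Favorable: 1 − Φ(1.941 − 2.208) = 60.5%
- Promising: the remaining 21.0%

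Power therefore cannot exceed 100 − 18.5 = 81.5%, whatever sample size follows.

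**4. Power of the whole procedure.** The formula for the raised sample size is only cited (reference 117), so three readings were run. Figures are from simulation with a final two-sample t-test, 3 million trials per reading.

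| Reading of the increase | Stop at CPmin | Same rule, continue at 128 below CPmin |
|---|---|---|
| Closed conditional-power formula, cap 292 | 77.3% | 83.9% |
| N solved for CP = 80%, cap 292 | 77.5% | 84.1% |
| Every promising trial to 292 (upper bound) | 78.8% | 85.3% |

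The third row is an upper bound because 9.4.6 takes the lower of the calculated size and 292. Normal integration gives 77.5, 77.8 and 79.0% with the stop.

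**5. Cost of the stop.** 83.9 − 77.3 = 6.6 points. As a share of stopped trials, 6.57/18.53 = 35% would have been significant at 128.

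**6. What would restore 80% with the stop in place.** Either a true effect of about 0.51-0.52 instead of 0.50, or a residual SD of 0.963-0.982. The latter means covariates explaining 1 − 0.982² = 3.6% to 1 − 0.963² = 7.3% of the variance (2.9-6.5% on the normal scale). At those residual SDs the stop still costs 6.3-6.5 points.

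**The case against.** **Nothing in 9.2 is arithmetically wrong.** It says it uses a t-test for simplicity, and that calculation reproduces. It does not expressly claim 80% for the three-zone procedure. This is true, but 80% is the only overall power the protocol gives, and the same document fixes the stop that lowers it. Operating characteristics may well appear in the statistical analysis plan, which was not available. The point does not depend on their absence, since both the 80% and the threshold are fixed in the protocol.

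**The primary analysis is not the t-test.** Section 2.2 describes age and early mRS as strong predictors of day-90 outcome, and both are covariates in the model. With a residual SD of 0.95, power with the stop is 81.3-82.4%. This is the strongest counterargument and it largely stands: the gap may well close. How far is uncertain, because entry restricts baseline mRS to 3 or 4, and the protocol states no assumed gain.

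**SD 1 may be cautious.** The pilot SDs were 0.66 and 0.46; at 0.66 throughout, power with the stop would be about 98%. The pilot was small, however, and the 80% is stated for SD 1.

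**The stop may be only advisory.** If it were ignored while the increase was used, power would be 83.9-85.3%. The decision rule in 9.4.6 is worded as an instruction, but the DSMB wording there and in 10.1.6 leaves room for doubt.

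**Giving up 6-7 points for early stopping is the sponsor's choice.** Agreed. The rule stops about 90% of trials under the null. The choice should be made with the figure in view.

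**Conclusion.** The concern holds. With a 0.5-point effect, SD 1 and a t-test, the design with its interim rules applied as written has 77-79% power, not 80%, under every reading of the increase rule that was tried. The shortfall is 1 to 3 points. Compared with continuing at 128 below CPmin, the stop costs 6 to 7 points. The result assumes the stop is always carried out and takes no credit for covariate adjustment. Type I error is not at issue: one-sided error under the null is 1.7-1.9% with the stop. The stated power should be corrected; the study does not need to be redesigned.

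**What to change.** **Needed.** In 9.2 and 9.4.6, state that 80% is the fixed 128-patient figure and that with the interim rules applied as written, power at 0.5 points is about 77-79% (SD 1, t-test). If the adjusted model is relied on to restore 80%, state the share of variance it is assumed to explain. State whether the stop is binding or advisory, so that the decision rule agrees with the DSMB wording in 9.4.6 and 10.1.6. Cost: two or three sentences and no patients.

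**Optional, for the sponsor to weigh.** Separate the futility bound from CPmin: continue at 128 just below CPmin, and stop only below a lower bound checked to keep whole-procedure power at 80% or more on the t-test scale. A bound of CP < 15% gives 80.8-82.3%. A bound of CP < 20% gives 79.9-81.3%, so it does not reach 80% under every reading.

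Moving to 15% lowers the share of null trials stopped from 90.3% to 84.5%. With the closed formula it raises expected sample size by about 3 patients: from 88.9 to 91.8 under the null, and from 132.9 to 136.2 at 0.5. One-sided type I error stays at 2.0-2.1%, and at most 2.4% with no stop at all.
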